The sample dimension was calculated using $\alpha = 0.05$ and the power of 80%. For the standard deviation (SD), the value of 0.8 mm obtained in a previous paper (Jepsen et al. 2013). Thus, study was powered to detect a minimum clinically significant difference in root coverage of 0.8 mm between the test and control treatments for root coverage after 6 months. On the basis of these data, the minimum needed number of

patients to be enrolled in this study resulted 28 for the test group (CAF) and 28 for the control group (CAF+ES).

Randomization, allocation concealment, and blinding

The randomization process was performed by an external person who did not participate in the study. Patients were assigned to one of the two treatment groups with the use of computer-generated randomization sequence. Allocation concealment was obtained using sealed coded opaque envelope containing the treatment to the specific subject. The sealed envelope containing the treatment assignment was opened immediately after the surgical procedure by the investigator responsible for the electrical stimulation protocol. The surgeon, patients and investigators who performed clinical measurements were blinded to procedures.

Surgical procedure

All surgical procedures were performed by a single operator ([name]). With a blade 15c (Surgi Blade® - Miami, FL - USA) two horizontal incisions were made at the bases of the mesial and distal papillae of the tooth, towards the adjacent teeth, taking care not to touch the adjacent teeth. From the end of the incisions, two divergent relaxing incisions were performed vertically in the apical direction that surpassed the mucogingival line so that the flap had mobility for coronary traction. A sulcular incision was performed in order to unite the releasing incisions and a split-full-split thickness flap was raised beyond the mucogingival junction (MGJ) (de Sanctis & Zucchelli 2007). After the root planing procedures were performed, the epithelial layer was removed from the incised papillae exposing the connective tissue. Before the flap was positioned coronally, the region was washed copiously with physiological solution to remove the clot allowing intimate contact of the flap with the recipient bed. Sling sutures (5.0 Vicryl™; Ethicon Inc, São José dos Campos, Brazil) were placed to stabilize the flap 2 mm coronal to CEJ, followed by interrupted sutures to close the releasing incisions.

Electric Stimulation Protocol

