The patients allocated in the CAF+ES group received the protocol for electrical stimulation. A unit consisting of a signal generator (Keysight Technologies., Inc., Santa Rosa-CA, USA), a power supply and circuit board, was assembled. Conductive electrodes for electrical current application were positioned on each side of the flap, at a

mean distance of 3 mm from the relaxing incisions and an alternating current with intensity of 100 μ A at 9 kHz, was distributed in order to traverse the operated region. Patients received the stimulus applications for 120 seconds, once a day for 5 consecutive days. The electrical current was optimized through an oscilloscope (Keysight Technologies., Inc., Santa Rosa-CA, USA). All applications were performed by a single researcher involved in the study ([name]). Patients randomized to the CAF group received the simulation of the electrical stimulation process.

Clinical Assessments

Clinical parameters were evaluated at baseline, 3 and 6 months postoperatively as follows: 1) full-mouth visible plaque index (FMPI) (Ainamo & Bay 1975), and presence or absence of visible plaque accumulation at the site included in the study (plaque index [PI]); 2) full-mouth sulcus bleeding index (FMBI) (Muhlemann & Son 1971), and presence or absence of bleeding on probing (BOP) at the site included in the study; 3) PD: measured in millimeters with a periodontal probe (XP23/UNC-15, Hu-Friedy, Chicago, IL); 4) relative GR (RGR): distance from the gingival margin to the incisal border of the tooth; 5) RCAL: measured as PD+RGR; 6) GR: measured at the mid-buccal aspect of the tooth (both RGR and GR quantified using a caliper with a precision of 0.01mm and a pair of dividers); 7) keratinized tissue width (KTW); and 8) keratinized tissue thickness (KTT): measured at the midpoint location between the gingival margin and mucogingival junction as previously described (Fernandes-Dias et al., 2015). A masked and calibrated investigator ([name]) carried out all clinical evaluations. The examiner calibration was performed for PD and RGR using Kappa statistic and intra-class correlation ($k = 0.88$ and $ICC = 0.81$, respectively).

Esthetic evaluation

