Levels of Cito / chemokines were determined by a multiplex immunoassay. Aliquots of each GCF sample were tested using a commercial human kit (Millipore Corporation, Billerica, MA, USA), in order to evaluate levels of the following inflammatory markers: interleukin (IL)-1 β , IL-6, IL-10, tumoral necrosis factor α (TNF α), macrophage inflammatory protein-1 α (MIP-1 α), and chemotactic protein for monocytes-1 α (MCP-1 α). In addition, matrix metalloproteinases (MMP)-2, MMP-9, tissue inhibitor of metalloproteinases (TIMP)-1, TIMP-2 and VEGF were also evaluated. Sample concentrations (antigens in gingival crevicular fluid samples) were estimated from the standard curve using standard kit proteins following manufacturer's instructions and expressed as pg / mL.

STATISTICAL ANALYSIS PLAN

Descriptive statistics were performed using mean \pm standard deviation (SD), and normality was tested using Shapiro-Wilk tests. The PD, RGR, CAL, KTT, KTW, and DH values and also inflammatory markers / growth factors were examined by two-way repeated measures ANOVA to evaluate the differences within and between groups, followed by a Tukey test for multiple comparisons when the Shapiro-Wilk p value was ≥ 0.05 . Data presenting Shapiro-Wilk p values < 0.05 were analyzed using Mann-Whitney tests (for intergroup comparisons) and a Friedman test (for intragroup comparisons). Postoperative discomfort, patient's esthetics measured through VAS and intergroup RES comparisons were analyzed by T-tests. The frequency of complete root coverage (CRC) was compared using χ^2 tests. For all tests a significance level of 0.05 was adopted.

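### The trial is sized on root coverage in mm at 6 months, but the SAP names no baseline-adjusted 6-month comparison for that outcome

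*Combined protocol and SAP*

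**What the plan says.** *Sample size* powers the trial for "a minimum clinically significant difference in root coverage of 0.8 mm between the test and control treatments for root coverage after 6 months", using alpha 0.05, 80% power and an SD of 0.8 mm taken from an earlier publication. It arrives at 28 patients per group. It does not say whether the 0.8 mm is the SD of a change or of a value at one visit. *Study Population* gives 60 patients with 60 recessions, in maxillary canines and premolars.

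*Clinical Assessments* states: "Clinical parameters were evaluated at baseline, 3 and 6 months postoperatively as follows". Two recession measures are taken: "relative GR (RGR): distance from the gingival margin to the incisal border of the tooth" and "6) GR: measured at the mid-buccal aspect of the tooth". Attachment level is given as "RCAL: measured as PD+RGR". Reliability is reported for two measures only: "The examiner calibration was performed for PD and RGR using Kappa statistic and intra-class correlation ($k = 0.88$ and $ICC = 0.81$, respectively".

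The *Statistical Analysis Plan* states: "The PD, RGR, CAL, KTT, KTW, and DH values and also inflammatory markers / growth factors were examined by two-way repeated measures ANOVA". Tukey comparisons follow. Where Shapiro-Wilk gives p < 0.05, the groups are compared by Mann-Whitney instead. The only root-coverage variable with its own test is complete root coverage, a yes/no outcome, by chi-square. GR and root coverage in mm are not listed. CAL is listed but not defined; presumably it is RCAL.

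**The concern.** The outcome that justifies the sample size is not tied to any named comparison. RGR can stand in for it, but a raw RGR value is crown length plus recession, so patients differ on it for reasons unrelated to treatment. The SAP refers to RGR values. It does not say which ANOVA term decides, whether a 6-month contrast is drawn, or whether the rank test is run on raw or change values.

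Two of the analyses that this wording permits are inefficient. Comparing raw 6-month RGR between groups (t-test, Mann-Whitney or Tukey on cell means) carries crown-length variance. The group main effect averages in the baseline visit, where no treatment effect can exist. At stake is the precision of the treatment estimate, and whether the report gives a 6-month difference in mm with a confidence interval at all.

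**Working it through.** **Plan's own figure.** A two-sided t-test with difference 0.8 mm, SD 0.8 mm, alpha 0.05 and 80% power needs 17 per group (16 by normal approximation). The stated 28 is not reproduced. That is a separate matter, and it leaves the trial larger than its inputs require. The figures below use 28 per group.

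**Inputs from the documents.** Difference 0.8 mm; SD 0.8 mm; 28 per group; visits at baseline, 3 and 6 months; RGR calibration ICC 0.81.

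**Assumptions.** 0.8 mm is the SD of change; the effect is 0.8 mm at both 3 and 6 months; the incisal edge is stable; baseline GR SD is 0.36 mm (3 mm plus a half-normal with scale 0.6); the 3-to-6-month residual correlation is 0.8; coverage is uncorrelated with baseline depth unless stated. The documents give no crown-length SD, so 0.5 and 0.8 mm are tried.

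**Formulas.** Power is from the noncentral t with 54 df. The 95% CI half-width is 2.005 × SD × √(2/28).

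1. *Change from baseline.* SD 0.8, standardised difference 1.0: power 95.7%, half-width 2.005 × 0.8 × 0.267 = 0.43 mm.
2. *ANCOVA on baseline GR.* Simulated power is about 95% with no correlation. If coverage correlates 0.5 with baseline depth, the residual SD is 0.8 × √0.75 = 0.69 and power is 98-99%.
3. *Group-by-time term.* Simulated with Greenhouse-Geisser correction: 96-97%. Closed-form check under compound symmetry: noncentrality 28 × 0.427 / (2 × 0.32) = 18.7 on 2 and 108 df, power 97.5%.
4. *Raw 6-month RGR.* SD = √(0.8² + 0.36² + crown²) = 1.01 mm for crown SD 0.5, and 1.19 mm for 0.8.
5. *Group main effect.* The difference is (0 + 0.8 + 0.8)/3 = 0.53 mm. The variance of the three-visit mean is crown² + 0.36² + (2 × 0.64 + 2 × 0.8 × 0.64)/9, so the SD is 0.80 mm for crown SD 0.5, and 1.01 mm for 0.8.
6. *Limit from the ICC.* With raw SD S, error variance is 0.19 S². A change contains two errors, so 2 × 0.19 S² cannot exceed 0.64, and S ≤ √(0.64/0.38) = 1.30 mm. The 6-month variance in this model, 0.62 S² + 0.64, is then also at most 1.30². For the main effect, the SD at the limit is 1.30 × √(0.81 + 0.19/3) = 1.21 mm.

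| Setting | Raw 6-month RGR: power | Half-width | Main effect: power |
|---|---|---|---|
| Crown SD 0.5 mm | 83% | 0.54 mm | 69% |
| Crown SD 0.8 mm | 70% | 0.64 mm | 49% |
| ICC limit, raw SD 1.30 mm | 62% | 0.70 mm | about 37% |

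**Where there is no shortfall.** The raw t-test keeps 80% power for 0.8 mm as long as raw RGR SD is at most 1.05 mm, which is a crown SD of about √(1.05² − 0.64 − 0.13) = 0.58 mm. If the 0.8 mm SD belongs to the raw 6-month value, the raw test has 95.7%. The main effect then has about 85% (compound symmetry, correlation 0.5, SD of the mean 0.65 mm).

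**At 30 per group** (the 60 patients split equally): raw test 85/73%, main effect 73/51%, group-by-time 97-98%, ANCOVA 96-97%.

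**The case against.** A reader might infer that the SAP contains no analysis of the sized outcome. The documents do not support that. If the incisal edge is stable, change in RGR is root coverage in mm, and RGR is in the ANOVA. A two-way model ordinarily includes group-by-time, which accounts for baseline and has 96-97% power, no worse than the ANCOVA's roughly 95% when coverage is unrelated to baseline depth. Tukey could also supply a 6-month between-group pair. All of this stands. It narrows the point to what is left unnamed: the link from RGR to root coverage, the deciding term, the 6-month contrast, and the scale for the rank test. A two-df interaction also yields no 6-month difference in mm with an interval, and Tukey on raw cell means carries crown-length variance.

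A second objection is that the low-power figures rest on a crown-length SD found nowhere in the documents and on reading 0.8 mm as the SD of change. That is fair. The range, the ICC limit and the conditions under which nothing is lost are therefore part of the result.

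A third is that making GR the primary measure would move the analysis from a measure with reported calibration to one without. That also stands, and the fix is built on RGR change for this reason.

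**Conclusion.** A free improvement, not an error that must be corrected. A reader might infer bias or an underpowered trial; neither follows. Randomisation protects all the between-group comparisons discussed, and an analysis with full power exists inside the named ANOVA. What holds is that the SAP does not commit to it. If 0.8 mm is the SD of change, the wording also permits a raw 6-month comparison with power between 83% and 62%, or a main-effect test with power between 69% and about 37%, over crown SDs from 0.5 mm up to the ICC limit. The raw comparison widens the interval half-width from 0.43 mm to between 0.54 and 0.70 mm. The ICC limit assumes that the calibration sites varied as the trial sites do. The loss shrinks or disappears if crown length varies little, or if 0.8 mm describes raw 6-month RGR. Under every reading, the plan still promises no 6-month difference in mm with a confidence interval for the outcome on which it was sized.

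**What to change.** - Name root coverage from baseline to 6 months, measured as change in RGR, as the between-group analysis for the sized outcome. Use ANCOVA with the baseline value (GR or RGR) as covariate, and report the adjusted mean difference in mm with its 95% CI. GR reduction is an acceptable alternative if the plan acknowledges that no calibration is reported for GR.
- If a rank test is used, apply it to change from baseline.
- If the ANOVA is kept, name the group-by-time term or the baseline-to-6-month contrast as the between-group test, not the group main effect or raw cell comparisons.
- State whether CAL is RCAL. If so, it contains RGR and should be treated in the same way.

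The cost is SAP wording and one degree of freedom. RGR and GR are already recorded at all three visits, and no additional patients are needed.

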**Electrical stimulation effect on coronally advanced flap
for the treatment of single gingival recession:
randomized controlled clinical trial**

UNESP – São Paulo State University. Dept. of Periodontology, College of
Dentistry

ClinicalTrial.org- NCT02987231

São José dos Campos, São Paulo - Brazil

August 15th, 2016

STUDY PROTOCOL

This investigation was a parallel, double-blind, randomized clinical trial. The study protocol (ClinicalTrial.org- NCT02987231) was approved by the Institutional Review Board at College of Dentistry – São José dos Campos, State University of São Paulo (1.679.369-UNESP). Each subject provided informed consent after a thorough explanation of the nature, risks, and benefits of the clinical investigation.

Study Population

Sixty patients from the Periodontology Clinic, UNESP—State University of São Paulo (São José dos Campos, Brazil), presenting 60 maxillary buccal gingival recessions in their canines and premolars were included in the study. The subjects were selected in the period between October 2016 and December 2017, according to the following eligibility criteria: 1) ≥ 18 years 2) periodontally and systemically healthy 3) FMPS and FMBS $\leq 20\%$ 4) single Cairo's class RT1 gingival recession (Cairo et al., 2011) in the maxillary canines or premolars ($\geq 3\text{mm}$ depth) at the buccal 5) presence of identifiable CEJ 6) no previous periodontal surgery at the affected teeth. Study exclusion criteria: 1) systemic problems that would contraindicate the surgical procedure; 2) patients taking medications known to interfere with the wound healing process or that contraindicate the surgical procedure; 3) smokers and pregnant women; 4) patients who underwent periodontal surgery in the area of interest; 5) patients undergoing orthodontic treatment.

Before surgery, Patients received oral hygiene instructions (roll technique) with a soft-bristled toothbrush to correct wrong habits related to the etiology of the recession. All participants received a session of prophylaxis and scaling. The surgical treatment was performed only when patients achieved adequate plaque control (full-mouth plaque score $\leq 15\%$)

Sample size

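### "CAL" in the SAP should almost certainly read RCAL; RCAL and RGR are analysed as raw values, so some planned between-arm tests carry avoidable crown-length variance (minor)

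*Combined protocol and SAP*

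**What the plan says.** Clinical Assessments defines RGR as "relative GR (RGR): distance from the gingival margin to the incisal border of the tooth" and the attachment measure as "RCAL: measured as PD+RGR". Recession itself is also recorded: "GR: measured at the mid-buccal aspect of the tooth". The schedule is "Clinical parameters were evaluated at baseline, 3 and 6 months postoperatively".

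The Statistical Analysis Plan states: "The PD, RGR, CAL, KTT, KTW, and DH values and also inflammatory markers / growth factors were examined by two-way repeated measures ANOVA". The purpose given is "to evaluate the differences within and between groups", with Tukey comparisons to follow. Where normality is rejected, the rule is "Data presenting Shapiro-Wilk p values < 0.05 were analyzed using Mann-Whitney tests (for intergroup comparisons", with a Friedman test within groups.

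The SAP does not expand CAL, and it mentions neither RCAL nor GR. It does not say which ANOVA effect tests treatment (group, or group by time). It also does not say whether the Mann-Whitney tests use visit values or changes from baseline.

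Study Population describes patients "presenting 60 maxillary buccal gingival recessions in their canines and premolars", one site per patient, so tooth types are mixed.

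**The concern.** There are two layers.

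**Name.** The variable collected and the variable analysed have different labels. PD + GR could also be formed from the data, so the text does not formally fix what CAL is.

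**Scale.** RGR and RCAL are measured from the incisal border. Each value therefore contains the tooth's distance from CEJ to incisal border, which has nothing to do with treatment and varies from tooth to tooth. If the arms are compared on raw values, that variation goes into the error term, and any chance difference in mean crown length goes into the estimate. In the non-normal branch, Mann-Whitney is the only between-arm test, so no interaction test is available there to remove it.

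At stake are the precision of the attachment and relative-recession comparisons, and the meaning of tabulated means: RCAL reported as CAL would look too large by a whole crown height.

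**Working it through.** **1. The plan's own figure.** No figure is given for attachment level. The Sample size section gives 28 per group for root coverage, from a difference of 0.8 mm, SD 0.8 mm, alpha 0.05 and 80% power. Taking alpha as two-sided (sidedness is not stated), n = 2 × (1.96 + 0.84)² × (0.8/0.8)² = 15.7, so 16 per group, or 17 by the exact t calculation. The stated 28 is not reproduced; with those inputs it gives about 96% power. That is a separate matter. It is noted here only because 96% is the starting point in step 4.

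**2. Which variable is CAL?** Clinical Assessments runs PD, RGR, RCAL, GR, KTW, KTT. The SAP runs PD, RGR, CAL, KTT, KTW. CAL stands where RCAL stood, directly after its two components, and GR, which a PD + GR version would need, is absent. A dropped R is the simplest reading.

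**3. What crown length does.** For tooth *i* at visit *t*, write RCAL(i,t) = A(i,t) + c(i). Here A is attachment level measured from the CEJ, signed, and c(i) is the fixed CEJ-to-incisal distance.

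- Change: RCAL(i,6) − RCAL(i,0) = A(i,6) − A(i,0). The constant cancels.
- Group by time, time, and Friedman use only within-tooth differences or ranks, so they do not change either.
- Single-visit variance: Var(RCAL) = Var(A) + Var(c), taking c as independent of A. The group main effect averages over visits, so c stays in it as well. The Shapiro-Wilk check on raw values is affected in the same way.
- Randomisation gives c the same expectation in both arms, so the expected arm difference is unchanged.

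The same algebra holds for RGR.

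**4. Illustrative size of the loss at 6 months.** Inputs: 28 per arm, difference 0.8 mm and SD of A 0.8 mm (both borrowed from root coverage), two-sided 0.05. Crown-length SD is assumed and ranged. SD of RCAL = √(0.8² + SD_c²). The standard error of the arm difference is that SD × √(2/28). The standard error of the chance imbalance in mean crown length is SD_c × √(2/28). Power uses the noncentral t with 54 degrees of freedom; Mann-Whitney power is from 4000 simulated trials on normal data.

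| SD_c (mm) | SD of RCAL | SE of difference | SE of crown imbalance | t power | Mann-Whitney power |
|---|---|---|---|---|---|
| 0 | 0.80 | 0.21 | 0 | 96% | 95% |
| 0.5 | 0.94 | 0.25 | 0.13 | 88% | 85% |
| 1.0 | 1.28 | 0.34 | 0.27 | 63% | 60% |
| 1.5 | 1.70 | 0.45 | 0.40 | 41% | 39% |

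**5. Check on the three-visit design.** Simulated two-group, three-visit repeated-measures ANOVA: 30 per arm, 2000 runs per scenario. Assumed values are between-patient SD 0.6 mm, within-patient SD 0.53 mm, and an arm difference of 0.6 mm at both postoperative visits. Results at SD_c 0.5 / 1.0 / 1.5 mm:

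- Group main effect: power about 0.63 without crown length, and 0.45 / 0.25 / 0.17 with it. This test is weak in any case, because it averages in a baseline visit with no expected difference: (0 + 0.6 + 0.6)/3 = 0.4 mm.
- 6-month Mann-Whitney on raw values: about 0.79 without, and 0.65 / 0.41 / 0.26 with.
- Group by time: 0.88 to 0.91, the same with or without crown length (F statistics agree to rounding error).
- 6-month change from baseline: about 0.86, the same with or without.

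**The case against.** The best defence is that CAL is plainly RCAL and that the planned ANOVA contains the right test. The group-by-time interaction asks whether the arms change differently, and crown length cannot touch it. Attachment level was not the outcome used for sample size, and the power figures rest on an assumed crown-length SD and on inputs borrowed from another outcome. Most of this stands. It does not fully answer the point, because the SAP never names the interaction as the treatment test and the non-normal branch has no interaction at all.

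A reader might infer something stronger: that CAL is a different variable from RCAL, so that the between-arm result in general depends on which is used, or that the choice was left open until results were known. The documents do not support this. The order of the list and the absence of GR favour RCAL, no PD + GR measure is mentioned anywhere, and the change-based results are identical under a constant offset. Nothing in the text shows a choice made after seeing results.

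One caveat concerns a PD + GR measure only. Under Surgical procedure, the flap is fixed coronal to the CEJ. If GR were recorded as zero whenever the margin lies coronal to the CEJ, PD + GR would no longer differ from RCAL by a constant, and changes could differ too. The documents do not say how this is recorded.

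**Conclusion.** The point holds as a minor one. The label is probably a slip and should be corrected. The substantive weakness is that RCAL and RGR are compared as raw incisal-referenced values with no named treatment contrast. Read literally, that exposes the group main effect, single-visit Tukey contrasts and raw-value Mann-Whitney tests to crown-length variance. The harm is lost precision and possible chance imbalance, not bias.

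The fall from 96% to 88%, 63% or 41% is an illustration. It rests on an assumed crown-length SD of 0.5 to 1.5 mm, on crown length being independent of attachment level, and on a 0.8 mm difference and SD taken from root coverage. It describes a stand-alone test at 6 months, not the full repeated-measures model. If treatment is judged by group by time or by change from baseline, crown length costs nothing.

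**What to change.** In the SAP:

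1. Replace CAL with RCAL, as defined under Clinical Assessments.
2. For both RCAL and RGR, make the between-arm comparison the 6-month value adjusted for its own baseline value. Change from baseline is an acceptable alternative; if it is non-normal, apply Mann-Whitney to the changes and not to the visit values. Change removes the crown-length term exactly; baseline adjustment lets the baseline value account for it.
3. If an attachment level based on PD + GR is reported, give it a separate label and state how GR is recorded when the margin lies coronal to the CEJ.

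Renaming alone would close the definition gap but leave the precision loss in both RCAL and RGR, which is why step 2 covers both. The cost is a few sentences. Every component is already scheduled at baseline and 6 months, so no new data or patients are needed.

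### Repeated measures ANOVA for the clinical outcomes, as usually run, discards observed 6-month values from any patient with a missed visit; a baseline-adjusted mixed model would keep them

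*Combined protocol and SAP*

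**What the plan says.** The Statistical Analysis Plan lists PD, RGR, CAL, KTT, KTW and DH, together with the inflammatory markers and growth factors, as variables to be "examined by two-way repeated measures ANOVA to evaluate the differences within and between groups", followed by Tukey comparisons. This applies when Shapiro-Wilk gives p of 0.05 or more. Otherwise groups are compared by Mann-Whitney and visits within a group by Friedman.

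The Clinical Assessments section sets the schedule: "Clinical parameters were evaluated at baseline, 3 and 6 months postoperatively as follows". The Patient-centered outcomes section gives the same three visits for DH. The comparison that the Sample size section powers is root coverage after 6 months.

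The Study Population section begins "Sixty patients from the Periodontology Clinic", and the Sample size section gives a minimum of 28 per group, 56 in all. The documents define no analysis set, no rule for missing values and no dropout allowance. They report no missed visits, and they do not say that incomplete patients are excluded.

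**The concern.** Classical two-way repeated measures ANOVA works on one full row per patient. With three visits, one empty cell normally removes the whole row. Two kinds of patient are affected:

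- A patient who misses month 3 but attends month 6 is removed from the comparison that matters most, although the value needed for it was recorded.
- A patient who attends month 3 and is then lost contributes nothing, although the 3-month result carries information about the 6-month result.

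A sentence on missing data would not cure this on its own. If the named method stays and is run on complete rows, recorded values are still thrown away.

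The normality rule adds a second problem. Mann-Whitney at 6 months needs only the 6-month value. A patient without a month-3 visit would therefore be in the 6-month comparison for an outcome that fails Shapiro-Wilk and out of it for one that passes. The set of patients compared should be fixed in advance and not follow from a normality test.

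At stake are some precision and, if the patients who fail to return differ between arms in their early result, some bias.

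**Working it through.** **Inputs from the documents.** 60 patients (Study Population); 28 per group as minimum, difference 0.8 mm, SD 0.8 mm, alpha 0.05, power 80% (Sample size); two follow-up visits (Clinical Assessments). The test is taken as two-sided, since the plan does not say. Baseline is taken as always observed, because the allocation envelope is opened only after surgery.

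**Assumed inputs.** The rate m at which each follow-up visit is missed, independently; the correlation between 3- and 6-month values; the dropout pattern in step 4.

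**1. The plan's own sample size.** n per arm = 2 × (1.960 + 0.842)² × (0.8/0.8)² = 15.7, so 16 with the normal approximation; the t test needs 16.7, so 17. The stated 28 is not reproduced from the stated inputs. That is a separate matter. It is relevant here only because it shows that 56 is not the number at which power reaches 80%.

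**2. Patients kept and patients with a 6-month value.** Complete = 60 × (1 − m)². With a 6-month value = 60 × (1 − m).

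| m (assumed) | Complete | With 6-month value | Observed 6-month values discarded |
|---|---|---|---|
| 2% | 57.6 | 58.8 | 1.2 |
| 5% | 54.2 | 57.0 | 2.9 |
| 10% | 48.6 | 54.0 | 5.4 |

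**3. Precision and power.** The standard error of an arm difference with N patients split equally is 0.8 × √(4/N). Discarding the incomplete rows inflates it by √[60(1 − m) / 60(1 − m)²] = 1/√(1 − m): 1.0% at m = 2%, 2.6% at 5% (0.217 against 0.212 mm) and 5.4% at 10% (0.230 against 0.218 mm). Two-sample t-test power for 0.8 mm with SD 0.8 mm is 95.0% at 27 per arm (about 54 complete), 92.4% at 24 per arm (about 49 complete) and 80.7% at 17 per arm.

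**4. Bias in an adverse scenario (all assumed).** No true effect, SD 0.8 mm at both visits, 3–6 month correlation 0.7. Control patients in the lowest third at month 3 are lost with probability 0.30; everyone else with probability 0.05.

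- Mean 3-month value, as deviation from the overall mean: lowest third −0.873 mm, remaining two thirds +0.436 mm.
- Control patients retained: (1/3) × 0.70 + (2/3) × 0.95 = 0.867. Loss is 13.3% in control and 5% in test, 9.2% overall.
- Mean 3-month deviation of retained controls: (0.233 × −0.873 + 0.633 × 0.436) / 0.867 = 0.084 mm.
- Shift at 6 months: 0.7 × 0.084 = 0.059 mm in favour of control.

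If the lower half instead of the lowest third is at risk, the shift is 0.068 mm with 11% overall loss. In simulation of both cut-offs the completer estimate was off by 0.06 to 0.07 mm. An estimate that uses the 3-month values of those lost was off by 0.00 mm. Type I error of the completer t test was about 6%.

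**The case against.** The strongest reply is that nothing has been shown to go wrong. The plan names a method, not an exclusion rule; whether incomplete rows are removed depends on how the analysis is run. No dropout or missed visit is documented. Sham stimulation and blinded patients make arm-specific dropout, which the bias example needs, less likely. A shift of 0.06 mm is about 8% of the 0.8 mm target and well under a standard error of about 0.22 mm. At 2% missed per visit only about one observed 6-month value is lost. All of this stands, and it limits the size of the point.

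It also stands that the limit does not reach every analysis. Friedman needs complete rows but is used only within groups; Mann-Whitney between groups does not. Complete root coverage, RES, patient esthetics and discomfort are tested by other methods. The crevicular fluid markers, with six time points and bloody strips discarded, are more exposed than the clinical outcomes.

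Two stronger readings are tempting. A reader might infer that the randomised comparison is lost. The documents do not support this: completers are still compared by randomised arm, and what is given up is the inclusion of all randomised patients. A reader might also infer that falling below 56 complete patients, only four fewer than 60, leaves the trial short of power. It does not: on the plan's own inputs, 17 per arm give 80%.

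The reply does not justify the method. Where visits are missed, its usual form discards recorded values, and an alternative that keeps them needs no new data.

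**Conclusion.** The point holds as a weakness in the choice of method for PD, RGR, CAL, KTT, KTW and DH. Run in the usual way, the planned ANOVA excludes patients whose 6-month value was recorded, and the normality rule can make the 6-month patient set differ between outcomes.

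The size is modest and conditional. With 2% to 10% of each follow-up visit missed, about 1 to 5 observed 6-month values are discarded and the standard error rises by 1% to 5%. Bias is about 0.06 mm under a deliberately adverse, arm-specific dropout pattern, and close to nil if visits are missed at random. If every patient attended every visit, no values are lost.

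These figures rest on assumed missed-visit rates, independence between visits and an assumed correlation of 0.7. They borrow the 0.8 mm SD that the plan gives for root coverage. Root coverage itself is not in the ANOVA list; RGR is the nearest listed variable.

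The change should be made, but the case for it rests on discarded data and possible bias and not on power.

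**What to change.** In the Statistical Analysis Plan, for PD, RGR, CAL, KTT, KTW and DH, replace the two-way repeated measures ANOVA with a linear mixed model for the 3- and 6-month values. Include arm, visit, arm-by-visit interaction and baseline value, with an unstructured covariance between the two visits. Include all randomised patients with any follow-up value, in the arm assigned, whatever number of stimulation or sham sessions they received. Report the 6-month arm contrast with its confidence interval.

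Make this the main analysis whatever Shapiro-Wilk shows, so that the patient set no longer depends on it. Mann-Whitney at 6 months can remain as a sensitivity analysis.

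The cost is a few sentences of SAP text and slightly more analysis work in standard software, with no new data. The downside is reliance on a missing-at-random assumption: the model corrects for dropout that depends on arm, baseline or the observed 3-month result, but not for dropout that depends on the unseen 6-month result. A pre-specified 6-month ANCOVA with a missing-data sensitivity analysis would also meet the main concern, but would use the 3-month values less fully.
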